##### **(2) Analysis of primary endpoints**

- **Local recurrence (LR):** Recurrence-free survival (RFS) curves will be plotted using the Kaplan-Meier method, and cumulative recurrence-free rates at 1, 3, 5,

and 10 years will be calculated. Univariate analysis using log-rank test; multivariable analysis using Cox proportional hazards regression (hazard ratios and 95% CI). When death is a competing risk for recurrence, cumulative incidence functions (CIF) and Fine-Gray competing risk models will be used.

- **Distant metastasis (DM):** Similarly, distant metastasis-free survival (DMFS) will be analyzed using Kaplan-Meier and Cox regression, with death as competing event.
- **Overall survival (OS):** Kaplan-Meier method will estimate median OS and 1-, 3-, 5-, 10-year survival rates. Cox regression will identify influencing factors.

### **(3) Analysis of secondary endpoints**

Secondary endpoints (demographic, tumor, treatment characteristics) will mainly be analyzed using descriptive statistics and between-group comparisons as described in (1). Additional exploratory analyses will include these variables as covariates in Cox or logistic regression to assess associations with primary outcomes. Latent class analysis may be used to identify subtypes based on tumor characteristics.

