##### **3.1.2 Secondary Objectives**

(1) Describe distribution characteristics: To determine the proportion of benign, borderline, and malignant PT in the Chinese population, as well as the distribution patterns of demographic and clinical features.

(2) Evaluate current treatment patterns: To depict the landscape and temporal trends of surgical procedures, margin status, lymph node surgery, and adjuvant radiotherapy/chemotherapy for PT in China over the past two decades.

(3) Quantify prognostic outcomes: To calculate local recurrence rates, distant metastasis rates, and tumor-specific mortality rates for the overall cohort and by histological grade, and to describe the patterns of PT outcomes.

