**(3) Recurrence-Free Survival (RFS)**

The time interval (in months) from the date of initial surgery to the date of first pathologically confirmed local recurrence. Patients without recurrence are censored at the date of last follow-up.

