## **5. Study Design**

### **5.1 Overall Design**

[figure not shown]
This is a multicenter, retrospective cohort study. Data will be collected from patients who underwent breast surgery at the Departments of Breast Surgery of the following eight participating centers between January 1, 2001, and December 31, 2023:

- Sun Yat-sen Memorial Hospital, Sun Yat-sen University
- The First People's Hospital of Foshan
- Sun Yat-sen University Cancer Center
- Peking University Shenzhen Hospital
- Foshan Women and Children's Hospital
- The First Affiliated Hospital of Guangzhou Medical University
- Zhongshan People's Hospital
- Shanwei People's Hospital

The expected sample size is approximately 3,500 patients. Using real-world data over nearly 20 years, the study will systematically describe the clinicopathological characteristics, treatment patterns, and long-term prognosis of breast PT in China, and identify independent risk factors through descriptive analysis, propensity score methods, competing risk models, and sensitivity analyses.

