### **(5) Bias control (as described in 5.3) – PSM, IPTW, E-value.**

### **(6) Stratified, subgroup, and sensitivity analyses**

- **Stratified analysis:** All primary analyses will be stratified by pathological grade (benign/borderline/malignant) to compare prognostic factors across grades.
- **Pre-specified subgroups:** Age (<35 vs. ≥35 years), tumor size (<5 cm vs. ≥5 cm), surgical procedure (segmental resection vs. minimally invasive rotary

excision, wide local excision vs. total mastectomy). Forest plots will display subgroup HRs with interaction P-values.

- **Sensitivity analyses:**
  - Complete case analysis vs. multiple imputation.
  - Varying PSM parameters (1:1 vs. 1:2 matching, caliper 0.1 vs. 0.2).
  - Separate analysis of recurrence definitions (ipsilateral chest wall/axilla only) to exclude misclassification.
  - Excluding patients with follow-up <6 months.
  - For OS, competing risk analysis with death from PT vs. other causes.

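### The exploratory analyses of LR, DM and OS may use logistic regression with no time horizon, which can bias odds ratios for covariates whose use changed materially over 2001–2023

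*Combined protocol and SAP*

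**What the plan says.** Section 1 names local recurrence (LR), distant metastasis (DM) and overall survival (OS) as the primary outcomes. Section 3.2.1 defines RFS, DMFS and OS as times from initial surgery. For RFS it adds: "Patients without recurrence are censored at the date of last follow-up". DMFS and OS are censored in the same way. Section 3.2.1 also lists LR and DM as crude percentages of the study population, and gives cumulative probabilities at 1, 3, 5 and 10 years.

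The main analyses in Section 5.4.2 (2) are time-to-event:
- LR: "multivariable analysis using Cox proportional hazards regression (hazard ratios and 95% CI"), with cumulative incidence and Fine-Gray models where death competes.
- DM: "analyzed using Kaplan-Meier and Cox regression, with death as competing event".
- OS: "Cox regression will identify influencing factors".

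Logistic regression enters only in Section 5.4.2 (3), for the demographic, tumor and treatment variables: "Additional exploratory analyses will include these variables as covariates in Cox or logistic regression to assess associations with primary outcomes". The plan does not say when logistic would be chosen over Cox.

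Section 5.1 takes surgery "between January 1, 2001, and December 31, 2023". No closing date for follow-up is given. The only minimum follow-up is a sensitivity analysis in Section 5.4.2 (6): "Excluding patients with follow-up <6 months". The adjustment factors named in Section 5.3 (5) do not include year of surgery or length of follow-up, though that list is open-ended.

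**The concern.** An ever/never logistic model asks whether an event was recorded, not when it occurred or how long the patient was observed. A patient operated on in 2001 can have over two decades in which to recur; one operated on in 2023 may have two years or so. If a covariate became more common over the period, its carriers have less time at risk and fewer recorded events, whatever its real effect. The odds ratio is then pulled downward: a null effect can look protective, a harmful one can shrink toward nothing, and a protective one can be exaggerated. A practice that fell out of use is distorted in the opposite direction.

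The variables open to this include those whose history the plan intends to chart in Section 3.1.2: "To depict the landscape and temporal trends of surgical procedures, margin status, lymph node surgery, and adjuvant radiotherapy/chemotherapy for PT in China". Section 3.1.3 wants the prognostic-factor results to inform individual follow-up and treatment, so a spurious odds ratio for a newer practice would matter even in an exploratory table. An open choice of model also lets the choice be made after results are seen.

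**Working it through.** **Plan's own figure.** Section 5.4.1 expects about 380 LR events. 3,500 × 0.11 = 385. From the grade mix: 0.7 × 7.1% + 0.2 × 16.7% + 0.1 × 25.1% = 10.82%, or 379 events. The figure reproduces.

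**Inputs.** From the plan: N = 3,500, 11% LR, surgery 2001–2023, two-sided α = 0.05. Assumed, because the plan does not give them: uniform surgery dates, data to end 2025, the trend in use, the hazard shape and the loss to follow-up.

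**Hand check: true HR 1.0, constant hazard, no loss.** Let s be surgery time, uniform on 0 to 23 years. Follow-up is u = 25 − s, with mean 13.5 and variance 23²/12 = 44.08.

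*Use rising from 5% to 50%* (mean 0.275):
- Covariance of use with follow-up = −(0.45/23) × 44.08 = −0.8625.
- Mean follow-up of users = 13.5 − 0.8625/0.275 = 10.36 years.
- Mean follow-up of non-users = 13.5 + 0.8625/0.725 = 14.69 years.
- A hazard of 0.00876 per year gives 11% overall: 1 − (e^(−2λ) − e^(−25λ))/(23λ) = 0.110.
- Averaging 1 − e^(−λu) over each group's surgery dates gives risks of 8.56% and 11.93%.
- OR = (0.0856/0.9144)/(0.1193/0.8807) = 0.69, although the covariate does nothing.
- With true HR 1.4 and the hazard rescaled to keep 11% overall, the risks are 10.85% and 11.06% and the OR is 0.98. The harm disappears.

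*Use rising from 20% to 35%* (same mean):
- Covariance = −(0.15/23) × 44.08 = −0.2875.
- Mean follow-up is 12.45 against 13.90 years.
- Risks are 10.19% and 11.31%, so OR = 0.89.

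**Range over hazard shape and loss.** Weibull shapes 1, 0.6 and 0.4, loss 0 or 8% per year, 300 simulated cohorts per scenario, univariable models:

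| Trend in use | OR at true HR 1.0 | Falsely protective, logistic | Power at HR 1.4, logistic |
|---|---|---|---|
| 5% to 50% | about 0.7–0.9 | about 10–81% | about 1–65% |
| 20% to 35% | about 0.88–0.99 | about 4–12% | about 50–85% |

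Cox under the 5% to 50% trend has power of about 80–87% at HR 1.4 and close to 5% two-sided rejections at HR 1.0. With flat use, logistic and Cox agree within about 2 points. The worst figures (OR 0.69, power 1%) come from the steep trend with constant hazard and no loss.

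**A second set of assumptions.** Use rising from 20% to 80%, constant hazard, data ending 1 to 3 years after the last surgery, true HR 1.5, 150 cohorts per scenario:
- Crude logistic: OR 1.02–1.08, power 0.08–0.13.
- Cox: HR 1.49, power 0.96.
- Logistic adjusted for year of surgery: OR 1.54–1.55, power 0.94–0.95.
- Logistic for LR by 5 years, among patients with that much potential follow-up: OR 1.51, power 0.65–0.69.

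**Where the bias vanishes.** With the same 20% to 80% trend but early recurrences (mean 1 to 2 years) and 3 to 5 years of follow-up after the last surgery, a true HR of 1.0 gives OR 0.98–1.00. With only 0.5 to 1 year after the last surgery, the OR is 0.92–0.98.

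**The case against.** The strongest reply is that little rests on this sentence. The main LR, DM and OS analyses use Cox and competing-risk methods; Section 5.3 (5) gives non-randomized treatment comparisons to propensity-score methods; Section 5.4.2 (6) reports subgroup results as hazard ratios. Logistic is one of two options in an additional exploratory analysis. That stands, and it limits the reach of the point.

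A reader might infer that the comparison involving minimally invasive rotary excision would be distorted. The documents do not support that: it appears as a subgroup whose stated output is hazard ratios. Nor does the plan predict that practice changed. It says trends will be described, and gives no direction or size.

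A reader might also infer that every covariate that changed over the period is biased. That is too strong: steepness of trend, timing of events, loss and length of follow-up after 2023 all govern the size. Adjusting for year of surgery removed the bias in the simulations. The plan could do this under its open-ended list of factors, but does not say so.

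Two further points stand. Logistic regression does fit the crude LR and DM percentages that Section 3.2.1 also lists as primary endpoints; those percentages ignore follow-up length in the same way, and changing Section 5.4.2 (3) will not cure that. And Cox was tested only with independent censoring and no calendar effect on risk, neither of which a retrospective cohort guarantees.

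None of this gives a reason to keep a logistic option without a horizon.

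**Conclusion.** The point holds as a limited one. Section 5.4.2 (3) permits a stated method that, in this design, can give a biased odds ratio for a covariate whose use changed materially over calendar time. The bias ranges from negligible to large enough to hide a true hazard ratio of 1.4, depending on assumptions the documents do not supply. The figures are for LR; for DM and OS the mechanism is the same, but the size was not worked out. The primary estimates and the subgroup hazard ratios are untouched. The change is worth making because it is specific and costs almost nothing, not because the study's main results are at risk.

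**What to change.** In Section 5.4.2 (3), delete *or logistic* for LR, DM and OS, so that these exploratory associations use the time-to-event models of Section 5.4.2 (2). This is one wording change; the event dates and the survival and competing-risk packages are already planned.

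If a binary model is wanted, state that it applies to a horizon the plan already names (1, 3, 5 or 10 years), use a method that handles censoring, such as inverse-probability-of-censoring weights or pseudo-observations, and include year of surgery as a covariate. Simply restricting to patients with full follow-up to the horizon is easier but loses power: about 0.65–0.69 against 0.96 for Cox in the constant-hazard example above.

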### **(4) Statistical adjustments**

- Multivariable model variable selection: backward stepwise regression (based on AIC) or LASSO penalized regression (when many variables).
- Proportional hazards assumption: tested using Schoenfeld residuals. If violated, stratified Cox, time-dependent covariates, or accelerated failure time models will be used.
- Multiple comparisons: For three primary endpoints (LR, DM, OS), each will be analyzed separately without multiple correction. For multiple exposure comparisons within the same endpoint, Bonferroni correction will be applied.

### **(5) Bias control (as described in 5.3) – PSM, IPTW, E-value.**

### **(6) Stratified, subgroup, and sensitivity analyses**

- **Stratified analysis:** All primary analyses will be stratified by pathological grade (benign/borderline/malignant) to compare prognostic factors across grades.
- **Pre-specified subgroups:** Age (<35 vs. ≥35 years), tumor size (<5 cm vs. ≥5 cm), surgical procedure (segmental resection vs. minimally invasive rotary

excision, wide local excision vs. total mastectomy). Forest plots will display subgroup HRs with interaction P-values.

- **Sensitivity analyses:**
  - Complete case analysis vs. multiple imputation.
  - Varying PSM parameters (1:1 vs. 1:2 matching, caliper 0.1 vs. 0.2).
  - Separate analysis of recurrence definitions (ipsilateral chest wall/axilla only) to exclude misclassification.
  - Excluding patients with follow-up <6 months.
  - For OS, competing risk analysis with death from PT vs. other causes.

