### **2.2.2 Epidemiology**

PT accounts for less than 1% of all breast tumors, and its epidemiological characteristics show distinct racial, regional, and age differences. As early as 1987, Chua et al. noted that PT incidence is higher in non-white populations, particularly in Asian women [13]. Asian PT patients are often younger (peak age 25-30 years), while Western patients are typically in their 40s. In 1993, Bernstein et al. reported that Latinas have a higher risk of PT compared to other racial groups. Age distribution varies by race, with Asian and Latina patients being significantly younger on average than non-Latina white patients [14]. Moten and Goldberg, in a large analysis of 1,202 patients with malignant PT from the SEER database, found that minority groups (Black, Hispanic, Asian) were diagnosed at significantly younger ages and had a higher risk of large tumors (>5 cm) and tumor extension beyond breast tissue [15].

Multiple studies show that the incidence of PT is approximately 2.1 per million women, accounting for 0.3%-1.0% of all breast tumors, with age at diagnosis concentrated between 35 and 55 years (median 45 years). Histologically, about 60%-75% of PT are benign, but both benign and malignant PT have the potential for local recurrence [3,5,6]. A systematic review and meta-analysis by Yu et al. of 52 real-world studies found an overall recurrence rate of approximately 12.6%, with risk increasing significantly with higher pathological grade: recurrence rates for benign, borderline, and malignant PT were approximately 7.1%, 16.7%, and 25.1%, respectively [10].

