##### **3.1.3 Exploratory Objectives**

(1) Analyze recurrence event patterns: To analyze the time distribution of recurrences, number of recurrences, and probability of pathological grade progression after recurrence, providing clinical insights into tumor progression mechanisms.

(2) Identify independent prognostic factors: To screen independent risk factors for local recurrence, distant metastasis, and survival using multivariable regression methods, and to compare differences in prognostic factors across pathological grades, providing evidence for personalized follow-up and treatment decisions.

(3) Lay the foundation for prospective studies: The database generated from this study will provide hypotheses and a theoretical framework for future prospective, interventional clinical research.

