### 5.4 Statistical Analysis

#### 5.4.1 Sample Size and Justification

This is a retrospective cohort study; sample size is not based on a pre-specified effect size. All eligible patients with breast PT from the eight centers between January 1, 2001, and December 31, 2023, will be included. Based on each center’s historical annual

caseload and pathology database searches, approximately **3,500 patients** are expected (benign:borderline:malignant  $\approx$  7:2:1).

This sample size is the largest multicenter real-world study in the PT field to date. According to the EPV (events per variable) rule, with local recurrence as the primary endpoint (estimated overall recurrence rate  $\sim$ 11%, yielding  $\sim$ 380 events), the sample size supports multivariable analysis of 30–40 independent variables, fully meeting the requirements for prognostic factor screening.

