#### **5.4.2 Statistical Analysis Plan**

Statistical analyses will be performed using R version 4.2.0 or higher (key packages: tidyverse, survival, rms, tableone, MatchIt, mice, tidycmprsk, mstate, etc.). The significance level  $\alpha = 0.05$  (two-sided), and 95% confidence intervals will be reported.

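### The plan sets out to compare prognostic factors between grades but specifies no factor-by-grade contrast; with limited events per grade, a shared moderate effect could be misread as grade-specific.

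*Combined protocol and SAP*

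**What the plan says.** Exploratory objective (2) in section 3.1.3 includes the aim to "compare differences in prognostic factors across pathological grades, providing evidence for personalized follow-up and treatment decisions". The method for it is one sentence in section 5.4.2 (6): "All primary analyses will be stratified by pathological grade (benign/borderline/malignant) to compare prognostic factors across grades". The next bullet lists pre-specified subgroups by age, tumor size and surgical procedure and adds: "Forest plots will display subgroup HRs with interaction P-values". Grade is not among those subgroups.

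Section 5.4.2 (2) reports Cox hazard ratios with 95% confidence intervals, and the opening of 5.4.2 sets alpha at 0.05 ("two-sided), and 95% confidence intervals will be reported"). Section 5.4.2 (4) selects variables by AIC-based backward elimination or LASSO, and applies Bonferroni to multiple exposures within one endpoint. The sample-size argument in 5.4.1 concerns the pooled cohort only: "380 events), the sample size supports multivariable analysis of 30–40 independent variables".

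**The concern.** Whether a factor matters differently in different grades is a question about the difference between log hazard ratios, that is, the ratio of hazard ratios. Separate fits within each grade do not estimate that quantity or give it an interval. Without a named contrast, the natural comparison is of which factors reach significance, or survive selection, in each grade. That comparison fails when power within a grade is moderate: a factor with the same effect everywhere will pass the threshold in some grades and miss it in others by chance. This holds even with one fixed covariate set and no variable selection.

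The results are meant to inform follow-up and treatment decisions, so a false grade-specific factor could carry weight beyond this report.

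**Working it through.** **Inputs from the documents.** Total: "The expected sample size is approximately 3,500 patients" (5.1). Grade mix 7:2:1 (5.4.1), so 2,450 / 700 / 350. Rates from 2.2.2: "recurrence rates for benign, borderline, and malignant PT were approximately 7.1%, 16.7%, and 25.1%, respectively". These are cited background rates, used here as planning rates. Alpha is 0.05, two-sided.

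**Assumptions not in the documents.** A common hazard ratio (HR) of 1.2 to 2.0 and a binary factor with prevalence p of 20-50%.

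**Step 1: reproduce the plan's event count.** 2,450 × 0.071 = 174.0; 700 × 0.167 = 116.9; 350 × 0.251 = 87.9. The sum is about 379, or 10.8% of 3,500. This agrees with the plan's figures of about 11% and about 380 events.

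**Step 2: power within each grade.** Schoenfeld's approximation: power ≈ Φ(√(d·p(1−p))·ln HR − 1.96), where d is the number of events. For HR 1.5 and p = 0.5:

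- benign: √(173.95 × 0.25) × 0.4055 = 2.67, power 76%
- borderline: √(116.9 × 0.25) × 0.4055 = 2.19, power 59%
- malignant: √(87.85 × 0.25) × 0.4055 = 1.90, power 48%

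**Step 3: probability that the grades disagree on significance.** This is 1 − P(significant in all three) − P(significant in none). For the same case: 1 − (0.762 × 0.592 × 0.476) − (0.238 × 0.408 × 0.524) = 1 − 0.215 − 0.051 = 73%.

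The table gives this probability in percent. In brackets is the value if the same 379 events were split equally, about 126 per grade.

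| Common HR | p = 50% | p = 30% | p = 20% |
|---|---|---|---|
| 1.2 | 43.7 (43.5) | 39.5 (39.4) | 34.0 (33.9) |
| 1.3 | 65.2 (64.6) | 59.9 (59.4) | 51.5 (51.2) |
| 1.5 | 73.4 (70.3) | 76.4 (74.2) | 75.4 (74.1) |
| 1.75 | 38.6 (31.3) | 50.4 (44.0) | 66.1 (61.7) |
| 2.0 | 13.6 (7.8) | 22.4 (15.3) | 39.8 (32.6) |

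Disagreement exceeds 50% for HR of about 1.23-1.67 at p = 50%, 1.26-1.75 at 30% and 1.30-1.90 at 20%. A survival simulation (log-rank test, 1,500 replicates per setting) gave 66%, 74% and 14% for HR 1.3, 1.5 and 2.0 at p = 50%, and 60%, 75% and 16% at p = 30%. The approximation is close except at HR 2.0 with p = 30%, where it runs somewhat high.

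**Step 4: the role of unequal event numbers.** The bracketed values show that inequality adds only about 0 to 8 points. The main cause is limited power within each grade. Inequality does tilt the direction. At HR 1.5 and p = 50%, significant in benign but not malignant has probability 0.762 × 0.524 = 40%, and the reverse 0.476 × 0.238 = 11%. With equal events, each would be 0.625 × 0.375 = 23%.

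**Step 5: the direct test.** A 2-df factor-by-grade test flagged a common effect 5.0% of the time in simulation. Its power for real differences follows from a noncentral chi-square with parameter Σ d·p(1−p)(b − b̄)², where b is the log HR in a grade and b̄ the weighted mean:

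- true HRs 1.0/1.5/2.0: parameter 7.61 at p = 50% (power 69%), 6.40 at p = 30% (61%)
- true HRs 1.5/1.5/1.0: parameter 2.77 at p = 50% (power 30%), 2.33 at p = 30% (26%)

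**The case against.** The strongest reply is that the plan never says grade differences will be read from within-grade significance. It reports hazard ratios with 95% confidence intervals, and a careful reader who sets these side by side need not be misled. That stands: the percentages above are probabilities of discordant P-values, not of false claims. But the plan offers no other rule for deciding that a factor differs, and three separate intervals do not supply an interval for the difference. Selection by AIC or LASSO, if run within grade, would also yield three lists that invite comparison by membership.

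The objective is exploratory, which limits the consequence, although its stated use is in follow-up and treatment decisions.

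The Bonferroni rule in 5.4.2 (4) might apply to these models; the text does not settle this. With ten factors (an assumption), disagreement at p = 50% would be about 26% at HR 1.3, 65% at 1.5 and 47% at 2.0. The figures move but the problem remains.

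A reader might infer two stronger things. One is that unequal event numbers alone create the problem; Step 4 shows that for local recurrence they do not. The other is that the plan will report grade-specific factors that do not exist, or will usually do so. The documents do not support that: it needs an inference rule that the plan does not state, and disagreement is the likelier outcome only for moderate effects.

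**Conclusion.** The omission is real: a named objective is to compare factors across grades, and no contrast that answers it is specified. For local recurrence, if a factor's effect is the same in all grades, significance would be discordant with probability about 52-76% for HR 1.3-1.5, 34-44% at HR 1.2 and 14-40% at HR 2.0. The plan therefore leaves open a misreading that is likely for moderate effects, and that would more often make a shared factor look specific to benign tumors than to malignant ones.

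These figures rest on the cited recurrence rates, the 7:2:1 mix, unadjusted two-sided 0.05, prevalence of 20-50% and Schoenfeld's approximation. For distant metastasis and overall survival the size cannot be given, because the documents state no metastasis or death rates for all three grades. Section 2.2.4 says that benign tumors have little effect on survival, so the imbalance there may be greater.

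**What to change.** In section 5.4.2 (6), name a short list of factors. For each endpoint, fit one pooled model with grade-specific baseline hazards and factor-by-grade interaction terms for those factors. Base any statement that a factor differs by grade on the 2-df interaction test and on the ratios of hazard ratios with 95% confidence intervals, shown beside the within-grade hazard ratios and their intervals. Add two sentences: significance in one grade but not another is not evidence of a difference, and a non-significant interaction does not show that effects are equal. Settle this before the database lock.

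The cost is one extra model per endpoint and some wording; no new data are needed. The drawback is the limited interaction power in Step 5 (26-69% in the two patterns examined), so fewer grade differences will be claimed.

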**3.2.2 Secondary Endpoints and Definitions**

**(1) Age at diagnosis** – Age (in years) when the patient was first diagnosed with breast PT.

- (2) **Menstrual status** – Premenopausal or postmenopausal.
- (3) **Childbirth history** – Yes or no.
- (4) **Family history of malignant tumors and PT** – Includes family history of breast cancer, other malignant tumors, and PT. Categorized as yes or no.
- (5) **Previous fibroadenoma surgery** – History of breast surgery for fibroadenoma. Categorized as yes or no.
- (6) **Maximum tumor diameter** – Largest tumor dimension (in cm) measured by preoperative imaging (ultrasound, etc.).
- (7) **Multifocality** – Solitary or multiple ( $\geq 2$  lesions in the same breast).
- (8) **Tumor location** – Left breast, right breast, or bilateral.
- (9) **Imaging findings** – Descriptions from breast and axillary ultrasound, mammography, breast MRI, chest CT, PET-CT, etc. (e.g., lobulated shape, margins, vascularity).
- (10) **Histological grade** – Benign, borderline, or malignant according to WHO criteria.
- (11) **Surgical procedure** – Type of initial surgery: wide local excision, total mastectomy, mastectomy with reconstruction, breast-conserving surgery, etc.
- (12) **Margin status** – Whether tumor cells are present at the surgical margin on postoperative pathology: negative (no residual tumor) or positive (residual tumor present). Margin distance (in cm) is also recorded.
- (13) **Adjuvant chemotherapy** – Whether adjuvant chemotherapy was given after surgery (yes/no), with details of regimen if available.
- (14) **Adjuvant radiotherapy** – Whether adjuvant radiotherapy was given after surgery (yes/no), with details of regimen if available.
- (15) **Axillary biopsy report** – Whether axillary lymph node biopsy (sentinel lymph node biopsy or axillary lymph node dissection) was performed, and the total number of lymph nodes examined and number of positive nodes recorded.

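### Effect modification by age and tumour size is tested only through single cuts at 35 years and 5 cm, although both are recorded continuously; if effects change gradually, this loses power

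*Combined protocol and SAP*

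**What the plan says.** In section 5.4.2 (6) the pre-specified subgroups for the two quantitative modifiers are "Age (<35 vs. ≥35 years), tumor size (<5 cm vs. ≥5 cm"). The output is stated as "Forest plots will display subgroup HRs with interaction P-values". That section gives no reason for either cut, and none of its listed sensitivity analyses varies them.

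The full values will be in the database. Section 3.2.2 defines age at diagnosis as "Age (in years) when the patient was first diagnosed with breast PT" and maximum diameter as "Largest tumor dimension (in cm) measured by preoperative imaging (ultrasound, etc".

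Elsewhere the two variables serve as adjustment covariates (section 5.3, item 5) or as covariates in exploratory regression (section 5.4.2, item 3). Their functional form is not stated, and no interaction with a continuous version appears. On precision, section 5.4.1 says that "sample size is not based on a pre-specified effect size". No power is given for any interaction test.

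**The concern.** A two-level split treats a 36-year-old and a 70-year-old as the same, and likewise a 5 cm and a 15 cm tumour. If a hazard ratio drifts with age or size, the split uses only part of the information about that drift. Interaction tests tend to be weak already, and nothing in the plan shows power to spare. A non-significant P-value on the forest plot could then be read as no difference by age or size when it partly reflects the split.

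What is at stake is the reading of a secondary layer of analysis. The primary estimates of recurrence, metastasis and survival are not affected.

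**Working it through.** **The plan's own figure.** The only related figure is about 380 local recurrences (section 5.4.1: about 3,500 patients, recurrence about 11%).

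- Direct: 3,500 × 0.11 = 385.
- From the 7:2:1 grade mix (section 5.4.1) and the recurrence rates of 7.1%, 16.7% and 25.1% (section 2.1): 3,500 × (0.7 × 0.071 + 0.2 × 0.167 + 0.1 × 0.251) = 174 + 117 + 88 = 379.

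The figure reproduces. It concerns the number of covariates a model can carry and says nothing about interaction power.

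**Inputs.** From the plan: two-sided alpha of 0.05 (section 5.4.2), the two cuts, and continuous recording. Assumed: a roughly normal modifier (diameter on the log scale), a linear interaction on the log-hazard scale, the share p below the cut, and the power of the continuous test.

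**Formulas.** With z_p the normal quantile at p, the share of information kept by a cut is E = φ(z_p)² / [p(1 − p)]. The power of the cut test is Φ(√E × (1.96 + z_power) − 1.96).

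Example, median split: E = 0.3989² / 0.25 = 0.637 and √E = 0.798. With 80% power for the continuous test, 0.798 × (1.96 + 0.842) = 2.235, and Φ(2.235 − 1.96) = 61%.

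| Split | E | Power of cut test (continuous test 80%) | Loss, points |
|---|---|---|---|
| 50:50 | 0.64 | 61% | 19 |
| 40:60 | 0.62 | 60% | 20 |
| 30:70 | 0.58 | 57% | 23 |
| 20:80 | 0.49 | 50% | 30 |
| 10:90 | 0.34 | 37% | 43 |

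**Dependence on the starting power.** For splits between 50:50 and 20:80, the loss is 9-13 points if the continuous test has 30% power, 15-22 at 50%, 19-29 at 70%, 17-28 at 90% and 13-24 at 95%.

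**Dependence on the number of events.** Hold fixed the interaction that gives 80% power at 380 events; the non-centrality then scales with √(events/380). Over the same range of splits, the loss for local recurrence is 15-21 points in benign tumours (about 174 events), 11-15 in borderline (117) and 8-11 in malignant (88). For metastasis, take 350 malignant cases. Rates of 6.5% and 62.5% (the range in section 2.1) and an assumed 20% give 23, 219 and 70 events; the losses are 2-3, 17-25 and 7-9 points.

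**Simulation check.** Cox models were fitted to 3,500 simulated patients with about 414 events, 40% exposed and an interaction hazard ratio of 1.34 per SD (600 runs per case). Continuous versus cut power was:

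- mean age 36.4: 83.3% v 65.3%
- mean age 40: 85.5% v 63.2%
- mean age 45: 83.0% v 52.8%
- mean size 3.7 cm (log scale): 81.5% v 55.0%
- mean size 5 cm (log scale): 82.2% v 62.7%

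The losses are 18-30 points, in line with the formula at that starting power. When the true effect was a step at 35 years (mean age 40), the order reversed: 67.0% continuous, 87.3% cut.

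**Cost of a spline as the test.** With the non-centrality that gives 80% power on 1 df, (1.96 + 0.842)² = 7.85, a joint test has about 71% power on 2 df and 64% on 3 df. Compared with the cut test at a median split (61%), the gain is about 10 or 4 points, where the 1-df linear test gains 19. If the 1-df test has 50% power, the 3-df test (34.5%) only equals the median split (34.6%).

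**The case against.** The strongest reply is that the shape of the effect is unknown. A step at the cut favours the split, as the simulation shows. In addition, 5 cm is not foreign to the document: section 2.2.2 uses tumours above 5 cm as a category of large tumour. Both points stand. They support keeping the cuts on the plot. They do not support making a step at one exact value the only alternative tested.

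Four stronger readings are tempting, and the documents do not support them.

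- **A loss of 20-30 points in general.** That range needs a 1-df linear test with roughly 70-80% power and about 20-40% of patients on the smaller side of the cut. The documents give neither. The plan also stratifies its primary analyses by grade, where events are fewer and the loss is mostly smaller. With a very unbalanced cut it is larger.
- **The same gain from any continuous method.** A joint spline test gives back much of it through its extra degrees of freedom.
- **A cut at 35 years that is clearly off-centre.** Section 2.2.2 gives a median of 45 years, but it also says Asian patients are often younger, with a peak at 25-30. In a Chinese cohort 35 could lie near the middle. The point does not need an off-centre cut, because a median split already loses about 36% of the information.
- **P-values that decide on tailored care.** Section 3.1.3 links individualised follow-up and treatment to independent prognostic factors and to their comparison across grades, as an exploratory aim. No decision rule is attached to the age or size interaction P-values.

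**Conclusion.** The point holds as a cheap improvement to a secondary analysis. The only planned tests of effect modification by age and size rest on one cut each, while the continuous values are available.

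For a gradual effect and a roughly normal modifier, the cut keeps between 64% (median split) and 49% (20:80) of the information. That takes a test with 80% power down to 61-50%. With 30-50% power to start from, the loss is about 9-22 points, and with few events it falls to single figures.

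The direction follows from the assumption of a gradual effect. The size also depends on the interaction effect, the starting power and the share on each side of the cut, none of which the documents state.

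**What to change.** In section 5.4.2 (6), before the database is locked, state:

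- The interaction P-value for age comes from a pre-specified 1-df term, exposure × continuous age. The one for tumour size comes from exposure × log(diameter).
- A restricted cubic spline with 3 knots (the rms package is already listed in section 5.4.2) is used only to check curvature and to plot the hazard ratio across the range of age and size.
- The rows below and above 35 years and 5 cm stay on the forest plots as descriptive display, without their own interaction P-values.

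The cost is a short addition to the plan and two extra models per endpoint, with no new data. The downside is lower power if the true effect is a step exactly at a cut.
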